#### 6.2.2 Study Pauses

Safety assessments are a continuous, real-time process. That is, the team reviews all AEs on conference calls twice a month while the study is enrolling. If study pause criteria as defined in Section 8.5.1 are met, enrollment and immunizations will be paused for SMC review. If the SMC decides that further enrollment and immunizations cannot be continued, the study will stop accrual but continue safety follow-up of all enrolled infants.

### **6.3 Criteria for Treatment Pause for Individual Participants**

For Dose Groups 1 and 2, who received a single dose of VRC01, there were no criteria to pause the treatment for individual participants. For Dose Group 3 and Cohort 2 of Dose Groups 4 and 5, the decision to hold administration of subsequent doses may be at the discretion of the site clinician in consultation with the P1112 study team.

## **6.4 Criteria for Treatment Discontinuation**

For Dose Groups 1 and 2, who received a single dose of VRC01, there were no criteria to discontinue the treatment for individual participants. For Dose Group 3 and Cohort 2 of Dose Groups 4 and 5, refer to Toxicity Management (Section 6.1.1) for criteria for treatment discontinuation. In addition, treatment discontinuation will occur if an infant is determined to be HIV-infected before he or she is 12 weeks old (see Section 6.6).

## **6.5 Criteria for Study Discontinuation**

- Infant does not receive the first VRC01, VRC01LS, or VRC07-523LS immunization.
- The mother or legal guardian refuses infant follow-up evaluations.
- The investigator determines that further participation would be detrimental to the participant's health or well-being.
- The participant fails to comply with the study requirements so as to cause harm to him/herself or seriously interfere with the validity of the study results.
- The study may be discontinued by the NIH, Office of Human Research Protection (OHRP), U.S. Food, and Drug Administration (FDA), the IMPAACT Network, IRB/EC or local government regulatory agency.

## **6.6 If an Infant is Determined to be HIV-Infected**

If an infant enrolled in P1112 has a positive HIV-1 NAT result at any time point, sites should notify the Protocol Team at [[contact]](mailto:[contact]) as soon as possible. Infants in Dose Group 3 with a positive HIV-1 NAT will not continue to receive VRC01 and will continue to be followed as per APPENDIX ID: Schedule of Evaluations (Dose Group 3) per the columns “Observation Period: Every 12 weeks after BF Cessation, HIV Diagnosis, and/or at Weeks 84 and 96.” Likewise, an infant identified as HIV-infected before he or she is 12 weeks old in Dose Groups 4 and 5 Cohort 2 would not receive a second dose of VRC01LS or VRC07-523LS and would continue to be followed per APPENDIX IF: Schedule of Evaluations (Dose Group 4, Cohort 2: breastfeeding) or APPENDIX IH: Schedule of Evaluations (Dose Group 5, Cohort 2: breastfeeding), respectively, per the column “Observation Following Dosing Period.” In addition, an infant with a positive HIV-1 NAT result in any Dose Group will undergo additional testing to confirm the infection and to collect blood samples for viral quantification and evaluation. The additional evaluations are listed in APPENDIX IC: HIV-1 Infected Infant Schedule of Evaluations (all dose groups)

## **7 EXPEDITED ADVERSE EVENT REPORTING**

### **7.1 Adverse Event Reporting to DAIDS**

Requirements, definitions and methods for expedited reporting of Adverse Events (AEs) are outlined in Version 2.0 of the DAIDS Expedited Adverse Event (EAE) Manual,

which is available on the Regulatory Support Center (RSC) website at <https://rsc.niaid.nih.gov/clinical-research-sites/manual-expedited-reporting-adverse-events-dails>

The DAIDS Adverse Experience Reporting System (DAERS), an internet-based reporting system, must be used for expedited AE reporting to DAIDS. In the event of system outages or technical difficulties, expedited AEs may be submitted via the DAIDS EAE Form. This form is available on the DAIDS RSC website at <https://rsc.niaid.nih.gov/clinical-research-sites/paper-eae-reporting>

For questions about DAERS, please contact NIAID CRMS Support at [[contact]](mailto:[contact]). Site queries may also be sent from within the DAERS application itself.

For questions about expedited reporting, please contact the DAIDS RSC Safety Office at [[contact]](mailto:[contact]).

## **7.2 Reporting Requirements for this Study**

The SAE Reporting Category, as defined in Version 2.0 of the DAIDS EAE Manual, are used for this study.

The study agent for which expedited reporting is required are: VRC01, VRC01LS, and VRC07-523LS.

In addition to the EAE Reporting Category identified above, other AEs that must be reported in an expedited manner are: immune complex disease.

## **7.3 Grading Severity of Events**

The Division of AIDS Table for Grading the Severity of Adult and Pediatric Adverse Events (DAIDS AE Grading Table), Corrected Version 2.1, July 2017, must be used with the exception of infant pain assessment. For pain assessment, a description of the pain grading to be used for IMPAACT P1112 may be found in the MOP. The DAIDS AE Grading Table is available on the RSC website at, <https://rsc.niaid.nih.gov/clinical-research-sites/dails-adverse-event-grading-tables>

## **7.4 Expedited AE Reporting Period**

The expedited AE reporting period for this study is as per the EAE manual, i.e., from enrollment of a trial participant to the end of trial follow-up for that participant.

After the protocol-defined AE reporting period, unless otherwise noted, only SUSARs as defined in Version 2.0 of the EAE Manual will be reported to DAIDS if the study staff become aware of the events on a passive basis (from publicly available information).

## 8 STATISTICAL CONSIDERATIONS

### 8.1 General Design Issues

This is an open label, multicenter, Phase 1 study to determine the safety and pharmacokinetic parameters of three subcutaneous, potent anti-HIV neutralizing monoclonal antibodies, VRC01, VRC01LS, and VRC07-523LS, in order to select a safe and PK-acceptable dose to be used in future efficacy clinical trials.

The study population is the newborns of HIV-1-infected women, who are  $\geq$  36 weeks gestation and are at increased risk for perinatal or post-natal HIV transmission (see Section 4.3.5 for definition of increased risk). The women do not receive study immunizations. After delivery, the mothers and their exposed neonates are checked for eligibility (see Section 4 for eligibility requirements for both mother and baby). If eligible, both the mothers and infants are enrolled. Only the infant is immunized with a subcutaneous injection(s) of VRC01, VRC01LS, or VRC07-523LS. Only the infants are assessed for safety and followed on the study.

The study will enroll 79 infants, with the aim of having approximately 62 evaluable infants: 10 of 13 (77%) each in Dose Groups 1-3 and 8 of 10 (80%) per cohort in Dose Groups 4 and 5. Evaluable infants must have received the required immunization(s) and have completed the required follow-up for the primary safety outcome measure for the relevant group (Day 28 evaluations for Dose Groups 1 and 2 and Cohort 1 in Dose Groups 4 and 5; Week 24 evaluations for Dose Group 3; and Week 16 evaluations for Cohort 2 in Dose Groups 4 and 5). .

Safety will be monitored in real time throughout the study. If none of the triggers listed in section 8.5.1 are met, the accrual and immunizations will proceed continuously, with no pause, until enrollment in the dose group has been completed. This will ensure that the study will remain open and all eligible infants will be enrolled and immunized in a timely manner.

If any safety triggers are met, subsequent enrollment and immunizations will be paused until the safety data are reviewed by the Study Monitoring Committee (SMC) (see Section 8.5.1) and they will advise the team on how to proceed.

Dose Groups 1-4 (Protocol Versions 1.0 - 3.0):

1) Initially, only Dose Group 1 was open to enrollment. Dose Group 1 accrued 13 women and their infants to provide at least 10 infants who received the immunization and completed study evaluations.

The infants received a single SC dose of 20 mg/kg of VRC01, as soon as possible after birth, and in all cases, less than 72 hours after birth.

Prior to opening Dose Group 2, the safety data through Day 28 after immunization for the first 10 infants immunized in Dose Group 1 were evaluated (see Section 8.5.1). After these infants had completed 28 days of follow up and had passed the safety criteria described in Section 8.5.1, AND after the enrollment in Dose Group 1 has been completed, AND the adult cohort using the dose of 40 mg/kg of VRC01 had been fully enrolled and all participants in it had completed day 28 evaluation, then

2) Dose Group 2 was opened and began accrual of a new set of 13 women and their infants, to provide at least 10 infants who received the immunization and study evaluations.

The infants in Dose Group 2 received a single SC dose of 40 mg/kg of VRC01, ideally as soon as possible after birth, but in all cases, less than 72 hours after birth.

Prior to opening Dose Group 3, the safety data through Day 28 after immunization for the first 6 infants immunized in Dose Group 2 were evaluated (see Section 8.5.1), After six Dose Group 2 infants completed 28 days of follow up and passed the safety criteria described in section 8.5.1, then

3) Dose Group 3 began accruing, concurrently with the remaining Dose Group 2 participants, a new set of 13 women and their infants, to provide at least 10 infants who received the immunizations and study evaluations.

The infants in Dose Group 3 received a SC dose of 40 mg/kg of VRC01, ideally as soon as possible after birth, but in all cases, not later than the 5th day of life, then doses of 20 mg/kg SC monthly for at least 24 weeks and no more than 72 weeks while breastfeeding.

Prior to opening Dose Group 4, all available safety data were evaluated (see Section 8.5.1).

4) Dose Group 4 accrued 21 women and their infants to two cohorts, to provide at least 8 infants in each cohort who will receive the immunizations and study evaluations. Enrollment into the two Dose Group 4 cohorts occurred sequentially (see **Error! Reference source not found.**, Section 3, and Section 6.2.1). An additional mother-infant pair was allowed to enroll because they had completed the screening when accrual limit was reached.

Infants in Dose Group 4 received a SC dose of VRC01LS as follows:

- Cohort 1 (non-breastfeeding): a single dose ideally as soon as possible after birth and within the first 72 hours of life.
- Cohort 2 (breastfeeding): a single dose ideally as soon as possible after birth, but in all cases, not later than the 5th day of life. A second dose of VRC01LS was administered at Week 12 if the infant has not achieved complete cessation of breastfeeding.

5) Dose Group 5 will accrue 20 women and their infants to two cohorts, to provide at least 8 infants in each cohort who will receive the immunizations and study evaluations. Enrollment into the two Dose Group 5 cohorts will occur sequentially (see **Error! Reference source not found.**, Section 3, and Section 6.2.1).

The infants in Dose Group 5 will receive a SC dose of VRC07-523LS as follows:

- Cohort 1 (non-breastfeeding): a single dose ideally as soon as possible after birth and within the first 72 hours of life.
- Cohort 2 (breastfeeding): a single dose ideally as soon as possible after birth, but in all cases, not later than the 5th day of life. A second dose of VRC07-523LS will be administered at Week 12 if the infant has not achieved complete cessation of breastfeeding.

Serious toxicity is not anticipated. However, safety will be monitored carefully, given that: a) study participants are newborns, b) they are born to women at increased risk for intrapartum HIV transmission and c) safety must be assessed before opening new cohorts.

## 8.2 Outcome Measures

All outcome measures apply to infants only.

### 8.2.1 Primary Outcome Measures

#### 8.2.1.1 Safety

Through Day 28 for Dose Groups 1, 2, Cohort 1 in Dose Groups 4 and 5; Week 24 for Dose Group 3; and Week 16 for Cohort 2 in Dose Groups 4 and 5:

- Death
- Grade 3 or higher adverse events
- Vaccine-related Grade 3 or higher adverse events
- HIV infection

#### 8.2.1.2 Pharmacologic

(See Section 9 for PK targets and parameters)

### 8.2.2 Secondary Outcome Measures

From the end of the observation period in the primary outcome measure through the end of follow-up:

- Death
- Grade 3 or higher adverse events
- Vaccine-related Grade 3 or higher adverse events
- HIV infection

From vaccine administration to end of follow-up:

- Development of anti-VRC01 antibodies (yes/no)
- Development of anti-VRC01LS antibodies (yes/no)
- Development of anti-VRC07-523LS antibodies (yes/no)

### 8.2.3 Other Outcome Measures

From vaccine administration to end of follow-up:

- The amount of VRC01/ VRC01LS/ VRC07-523LS in oral secretions.

Measured in infants determined to be HIV-infected from vaccine administration to end of follow-up:

- The neutralization sensitivity of the infant and maternal virus
- The amount of HIV-1 provirus in PBMC and plasma HIV-1 RNA (measured in copies/mL)
- Serum neutralizing titer

## 8.3 Randomization and Stratification

There will be no randomization or stratification of participants.

## 8.4 Sample Size and Accrual

Both mothers and infants are enrolled in the study, but only infants receive the VRC01, VRC01LS, or VRC07-523LS immunization(s) and are followed on the study. The study will enroll 79 mother-infant pairs: 13 in each of Dose Groups 1-3 and 10 in each cohort in Dose Groups 4 and 5, with the aim of having 10 evaluable infants in each Dose Group 1-3 and 8 in each cohort in Dose Groups 4 and 5. Evaluable infants must have received the required study immunization(s) and have completed follow-up for the primary safety outcome measure (Day 28 evaluations for Dose Groups 1, 2 and Cohort 1 from Dose Groups 4 and 5; Week 24 evaluations for Dose Group 3; and Week 16 evaluations for Cohort 2 in Dose Groups 4 and 5). This assumes a maximum missing data rate of 23% in Dose Groups 1-3 and 20% in Dose Groups 4 and 5. Non-evaluability could be due to losses to follow-up, missed visits or problems with laboratory samples. Note that infants who do not receive the first immunization will be replaced.

Safety data will be assessed as described in Section 8.5.1. If any of the safety criteria are triggered, enrollment and further immunizations will be temporarily stopped until the SMC reviews the data and advises the protocol team on how to proceed. Section 8.5.1 discusses the error probabilities associated with the safety criteria and Section 8.6.1.2 discusses the precision that the sample size will provide for estimating AE rates and PK success rates. The sample size is based on target precision for the estimation of key safety and PK parameters. The calculations are located in Section 8.6.1.2 for ease of discussion.

We had anticipated that all participants in Dose Groups 1 and 2 would be enrolled within 2 years after Version 1.0 was opened to accrual. In fact, enrollment into both dose groups was more rapid than anticipated: taking less than 9 months to reach full accrual of each dose group. Likewise, Dose Group 3 reached full accrual within approximately 4 months. We had anticipated that Dose Group 4 would be fully enrolled within 1 year of that dose group being opened to accrual. However, this group also reached full accrual much faster than expected, within 6 months. It is anticipated that both cohorts in Dose Group 5 will be enrolled within 1 year after Version 4.0 opens to accrual.

## 8.5 Monitoring

The safety and tolerability of the VRC01, VRC01LS, and VRC07-523LS monoclonal antibodies are monitored by means of adverse events and toxicity reports presenting laboratory and clinical data collected throughout follow-up for the infants enrolled. It is required that these data be entered into the database within 48 hours of the time at which the results of the laboratory tests or clinical examinations become available. The accrual and toxicity reports compiled by the Data Management Center are discussed by the protocol team, including the medical officers and the representatives of the VRC, on regularly scheduled conference calls. After the first infant enrolled into Dose Group 3 reached the Week 24 milestone, the team began reviews of available safety data of adult and pediatric protocols of VRC01 (from P1112 database and most recent safety reports available from the other protocols) every 6 months. These reviews will continue and include infants in Dose Groups 4 and 5 and data on VRC01LS and VRC07-523LS. There will be no pause in either enrollment or in administration of immunizations during these reviews.

The attribution of relationship of serious adverse events to study product is discussed on the team calls and the relationship determined by the study team, taking into account the site and the Medical Officer's assessment of the event. Interpretation of VRC01, VRC01LS, or VRC07-523LS relationship to adverse events is based on the type of event, the relationship of the event to the time of immunization, the known biology of the monoclonal antibody and the investigators' medical judgment. Gradation of relationship uses the following terminology: "not related," "probably not related," "possibly related," "probably related," or "definitely related."

In addition to regularly scheduled toxicity reviews by the protocol team, the study is monitored by an independent Study Monitoring Committee (SMC) according to IMPAACT Standard Operation Procedure (SOP) on Study Data and Safety Monitoring. The committee meets via conference call to review relevant data as described in the sections below.

### 8.5.1 Stopping Rules for Safety

Stopping rules have been and will be applied in order to protect the study participants from unnecessary exposure to the monoclonal antibody, should the safety profile prove unacceptable in this population. The evaluation of safety for the purpose of applying these guidelines will be based on data:

- through the first 28 days after immunization for Dose Groups 1, 2, and Cohort 1 of Dose Groups 4 and 5;
- on data through the first 8 weeks after the first immunization for Dose Group 3, which reflects the time point when this group would have received more immunizations than Dose Groups 1 and 2;
- on data through the first 28 days after the second immunization in Dose Groups 4 and 5, Cohort 2 (Week 16).

Due to the fact that infant hyperbilirubinemia is common in the first four to five weeks of life, especially during breastfeeding, and that Grade 3 neutropenia and anemia are common in infants on ARVs, these toxicities will not be counted in the safety evaluation algorithm presented below.

NOTE: If at any time during the study the triggers below are met, the study will be paused for evaluation, as described below and an SMC review performed within 7 days. The SMC will decide what additional data they would like to see and advise the study team on how to proceed.

To assess the early safety of the initial doses of VRC01, VRC01LS, and VRC07-523LS monoclonal antibodies, data from the first 6 infants immunized and followed through day 28 in Dose Groups 1, 2, and Cohort 1 of Dose Groups 4 and 5 will be examined.

Similarly, the early safety of the multiple dose regimen of VRC01 monoclonal antibody in Dose Group 3 will be assessed based on data from the first 6 infants immunized and followed through Week 8. The early safety of the multiple-dose regimen of VRC01LS in Dose Group 4 (Cohort 2) and of VRC07-523LS in Dose Group 5 (Cohort 2) will be assessed based on data from the first 6 infants who have reached 28 days after the second dose (Week 16).

- If any of the infants dies or has a life-threatening adverse event or any Grade 4 event that is possibly, probably or definitely attributable to the VRC01, VRC01LS, or VRC07-523LS immunization, or
- If two or more of the six infants have a Grade  $\geq 3$  adverse event at least possibly related to the VRC01, VRC01LS, or VRC07-523LS immunization (excluding Grade 3 neutropenia and anemia, and hyperbilirubinemia), then future enrollment and immunizations will be stopped.

If these triggers are met, the team will confer with the SMC, which will judge whether enrollment and immunizations can be continued. Note: for deaths and grade 4 life-threatening events that are assessed by the protocol team as probably not related, immunizations will continue. However, an SMC review to determine if it is safe to continue immunizations must occur within 7 days of the team's awareness of the event.

If the ongoing monitoring process reveals that a dose group has already failed the safety criteria, then further enrollment and immunizations will be suspended, and an SMC review will be performed immediately (within seven days).

If the SMC decides that further enrollment and immunizations cannot be continued, the study will stop accrual but continue safety follow-up of all enrolled infants.

Subsequent to the initial safety evaluation of each dose group, if the toxicity among the additional infants who have been immunized while waiting for the first 6 to reach the evaluation time point would increase the rate of Grade  $\geq 3$  adverse events at least possibly related to the VRC01 VRC01LS, or VRC07-523LS immunization (excluding

Grade 3 neutropenia and anemia) to over 30%, then future enrollment and immunizations will be paused. For example, if only one of the first 6 infants enrolled had a Grade  $\geq 3$  adverse event at least possibly related to the VRC01, VRC01LS, or VRC07-523LS immunization, this is not enough to trigger the stopping rule. But if the next two infants each have a Grade  $\geq 3$  adverse event at least possibly related to the VRC01, VRC01LS, or VRC07-523LS immunization, this would represent a 37.5% (3/8) rate of such events, and because this is higher than 30%, the study will be paused for safety. The team will confer with the SMC, which will judge whether enrollment and immunizations can continue.

Given the relatively small sample size, the information available for preliminary safety decisions will be imperfect. Two types of sampling errors are possible:

- 1) In a group where the true rate of toxicity is too high to warrant increased exposure to the current VRC01, VRC01LS, or VRC07-523LS dose, the sample data may pass the safety guidelines;
- 2) In a group where the true rate of toxicity is low enough that further exposure to the current VRC01, VRC01LS, or VRC07-523LS dose is warranted, the sample data may fail the guidelines.

The extent to which the safety guidelines protect against the errors described above can be assessed by examining various hypothetical rates of "true toxicity" which could occur, if the study medication were used extensively among the participant population at the dose levels under question. The hypothetical situations presented in Table 6 range from conditions under which a given dosing regimen would cause a high incidence of severe and life-threatening adverse events to conditions under which severe adverse events would be relatively rare and would not be life-threatening. For each of these hypothetical situations, we assume that a sample of six participants is drawn from the participant population and that the safety guidelines, summarized above, are followed.

Please note that the probabilities presented below would not apply if data from more than six infants were used.

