**Table 6: Probability of Meeting Safety Review Trigger Under Potential Rates of True Toxicity (N=6)**

True Toxicity Rates		Probability of Meeting Safety Review Trigger
Grade $\geq$ 3 adverse events at least possibly related to the VRC01, VRC01LS, or VRC07-523LS immunization, excluding Grade 4 events probably or definitely attributable to the study immunization	Life-Threatening adverse event or Grade 4 events probably or definitely attributable to the VRC01, VRC01LS or VRC07-523LS immunization	
.50	.00	.89
.50	.05	.94
.50	.25	1.00
.25	.00	.47
.25	.05	.63
.25	.25	.83
.05	.00	.03
.05	.05	.29
.05	.25	.83
.00	.05	.26
.00	.25	.82

For example, Table 6 shows that there is a 94% chance of failing the safety guidelines under conditions in which the true rate of life-threatening toxicity is 5% and the rate of non-life-threatening toxicity is 50%. Assuming that a dosing regimen associated with this extent of severe toxicity would be unacceptable, the 6% chance of passing the safety criteria under these conditions would represent sampling error. Note that the true rate of Grade 3 events would have to be quite high to provide a strong probability of pausing the study at a dose where there is no life-threatening toxicity and no Grade 4 events at least probably attributable to VRC01, VRC01LS, or VRC07-523LS. This is considered acceptable, since a larger sample size would be needed to increase the probability of pausing the study at lower rates of Grade 3 events, and this would entail exposing greater numbers of children to an experimental dose, which may be either toxic or subtherapeutic.

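### The two-of-six stopping trigger excludes hyperbilirubinemia to Week 16 in Dose Group 5 Cohort 2, on a reason that covers only the first four to five weeks of life

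*Protocol*

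**What the plan says.** All of the rules are in Protocol Section 8.5.1.

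- **Reason.** Hyperbilirubinemia is set aside because "infant hyperbilirubinemia is common in the first four to five weeks of life, especially during breastfeeding". Grade 3 neutropenia and anemia are set aside because they are common in infants on antiretrovirals.
- **Lead-in.** It then says that "these toxicities will not be counted in the safety evaluation algorithm presented below". Neutropenia and anemia carry a grade; hyperbilirubinemia carries neither a grade nor an end date.
- **Window.** For Cohort 2 of Dose Groups 4 and 5 the evaluation is "on data through the first 28 days after the second immunization in Dose Groups 4 and 5, Cohort 2 (Week 16"). For Cohort 1 of those groups it is 28 days.
- **Grade 4 trigger.** One infant with "any Grade 4 event that is possibly, probably or definitely attributable to the" product is enough. No exception is stated.
- **Two-of-six trigger.** Two or more of the first six infants with a related Grade 3 or higher event, "excluding Grade 3 neutropenia and anemia, and hyperbilirubinemia), then future enrollment and immunizations will be stopped".
- **Over-30% rule for later infants.** Its exclusions are shorter: "Grade 3 neutropenia and anemia) to over 30%, then future enrollment and immunizations will be paused". Hyperbilirubinemia is not named.
- **Consequence.** "If at any time during the study the triggers below are met, the study will be paused for evaluation", with review by the Study Monitoring Committee (SMC) within 7 days.

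Appendix IH, footnote 9, puts total bilirubin in the chemistry panel. The same footnote treats jaundice as a sign of a hepatic event that calls for extra ALT and AST.

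**The concern.** The exclusion lasts longer than its justification. Common neonatal jaundice is a good reason not to let early bilirubin values pause a trial. It is no reason to disregard a bilirubin rise at three months of age, after a second dose of a new antibody. The remark about breastfeeding qualifies the early period and does not extend it.

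In Dose Group 5 Cohort 2 the Week 16 review is the early safety check on the two-dose regimen. As written, its main numerical trigger cannot respond to a related Grade 3 bilirubin event after the second dose. The mixed wording adds a second problem. Two careful readers could disagree about whether one related Grade 4 bilirubin event pauses dosing, and that should be settled before such an event occurs.

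**Working it through.** **1. Which groups are affected.** The 28-day windows (Dose Groups 1 and 2, and Cohort 1 of Dose Groups 4 and 5) lie essentially within the four to five weeks, so there the exclusion fits its reason. The mismatch arises in Dose Group 3 (8 weeks) and in Cohort 2 of Dose Groups 4 and 5 (Week 16). Under Version 4.0 only Dose Group 5 Cohort 2 was still to be enrolled.

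**2. Share of the window without a stated reason.** Week 16 is 16 × 7 = 112 days. Five weeks is 35 days, and (112 − 35)/112 = 77/112 = 69%. With four weeks, (112 − 28)/112 = 84/112 = 75%.

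**3. Where bilirubin is measured.** The Appendix IH table is hard to read in extracted form, so I checked the chemistry row against its blood-volume totals (mL):

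| Visit | Sum of rows | Stated total | Chemistry |
|---|---|---|---|
| Day 28 | 1+1+1+2+(0–1) = 5–6 | 5–6 | yes |
| Week 8 | 3+(0–1) = 3–4 | 3–4 | no |
| Week 12 | 1+1+1+3+2 = 8 | 8 | yes |
| Week 14 | 1+1+2+2 = 6 | 6 | yes |
| Week 16 | 2+2 = 4 | 4 | no |

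Two of the three scheduled post-dose bilirubin tests in the window fall after week five. Week 14 is the only one after the second dose.

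**4. The plan's own figures.** Table 6 ("Probability of Meeting Safety Review Trigger Under Potential Rates of True Toxicity (N=6")) gives the chance of meeting a trigger. With a the rate of related Grade 3 type events, b the rate of life-threatening or related Grade 4 events, and n = 6:

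P = 1 − [(1−a−b)^6 + 6a(1−a−b)^5]

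- a = .05, .25, .50 with b = 0: .033, .466, .891 (Table 6: .03, .47, .89)
- a = 0 with b = .05, .25: .265, .822 (Table 6: .26, .82)
- a = .50, b = .05: .936 (Table 6: .94)

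The formula matches 10 of the 11 rows. The .25/.25 row (.83 stated, .94 by this formula) is not used here.

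**5. What the exclusion changes.** The smallest case shows it. One other related Grade 3 event plus one related Grade 3 bilirubin rise at Week 14, in different infants, is 2/6 and a pause if both count. As written it is 1/6 and no pause. For a related Grade 4 bilirubin event at an assumed true rate of 5% or 25%, the trigger probability is .26 or .82 if the Grade 4 bullet governs, and 0 if the lead-in does. The documents give no rate of related hyperbilirubinemia, so these rates are illustrations.

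**6. Does the over-30% rule fill the gap?** Read literally, it counts bilirubin. But it applies after the initial evaluation and needs more events: 3 of 7, 3 of 8, 3 of 9 or 4 of 10 (3/10 is exactly 30%, not over). It does not restore the two-of-six check.

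**7. What a pause could still prevent.** Dose Group 4 Cohort 2 opened on 7 December 2017 and Dose Group 4 was full by 1 February 2018, at most 56 days. Assume that 10 infants enter Dose Group 5 Cohort 2 evenly and that all are due a second dose. Infant k enters on day (k−1) × T/9, is due dose two 84 days later, and reaches Week 14 after 98 days. The trigger is met at infant 2 at the earliest and at infant 6 at the latest.

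| Accrual T (assumed) | Lag from visit to pause | Pause day (infant 2; infant 6) | Second doses left |
|---|---|---|---|
| 56 days | none | 104.2; 129.1 | 6; 2 |
| 56 days | 14 days | 118.2; 143.1 | 4; 0 |
| 182 days | none | 118.2; 199.1 | 8; 4 |
| 182 days | 14 days | 132.2; 213.1 | 7; 3 |

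The 14-day lag reflects the twice-monthly team calls (Section 6.2.2). Section 8.5 also allows 48 hours for data entry. The protocol expects both Dose Group 5 cohorts to fill within a year, so 182 days is plausible for one of them.

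**The case against.** The strongest reply is that little is lost. ALT and AST events still count, so a hepatic signal goes uncounted only if bilirubin rises alone. Section 6.1 requires all Grade 3 or higher events to be reported, the team reviews events twice a month while enrolling, and Sections 6.1.1 and 6.3 allow an infant's next dose to be held with no bilirubin exception. The documents report no bilirubin signal: transient AST and ALP rises in rats given VRC01, and one adult Grade 4 liver-enzyme event in VRC605 that was attributed to another drug.

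Most of this stands, and it is why the effect is modest. It does not close the gap. A Cohort 2 infant with a Week 14 event has no further dose to hold, so only a group-level pause protects the infants still awaiting theirs. Team calls rest on judgment, whereas the trigger compels a pause and an SMC review.

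Three stronger readings are tempting, and the documents support none of them:

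- **That hyperbilirubinemia is out of every stopping rule.** The Grade 4 bullet has no exception and the over-30% rule does not list bilirubin. Read literally, both count it. Against the lead-in they show ambiguity, not a proven total exclusion.
- **That the fall from .47 or .89 to 0 measures the harm.** Any excluded event has probability 0 of meeting the trigger, by definition, and 25% to 50% are not rates that the documents suggest for bilirubin.
- **That a trigger would reliably spare two to six second doses at the pace of Dose Group 4.** That assumes the visit, the attribution and the pause all fall on one day. With a 14-day lag it is four down to none.

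**Conclusion.** The point holds in limited form. In Dose Group 5 Cohort 2, related Grade 3 or higher bilirubin events at Weeks 12 and 14 cannot count toward the two-of-six pause, although the stated reason ends at week five. The lead-in, the Grade 4 bullet and the over-30% rule also disagree about bilirubin.

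The size is modest: one analyte in one 10-infant cohort. About 69% to 75% of the window lacks a stated reason. The benefit of a pause ranges from none to several second doses. That range depends on assumed accrual, even spacing, reporting lag and all infants still breastfeeding at Week 12. The change is worth making because the rule governs newborns, the wording is ambiguous and the correction keeps the sponsor's own reasoning. It is not evidence of a hepatic risk.

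**What to change.** Use one exclusion list in the lead-in, the two-of-six trigger and the over-30% rule: *excluding Grade 3 neutropenia, Grade 3 anemia, and hyperbilirubinemia on samples taken up to five weeks of life or at the Day 28 visit*.

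- The Day 28 visit is named because it can fall at about day 36 of life (dose by Day 5, plus 28 days, plus the 3-day window).
- Tying the exclusion to the sample date means that any related Grade 3 or higher value on a later sample counts, including an early rise that persists or worsens after the second dose. It also avoids disputes about onset, since no chemistry is scheduled between Day 28 and Week 12.
- State that related Grade 4 hyperbilirubinemia after that period counts under the Grade 4 bullet. Whether it should also count in the first five weeks is a trade-off for the sponsor: it would let one possibly related neonatal event pause the study at an age when jaundice is common. Either answer should be written down.

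**Cost.** A few words in Section 8.5.1 and no extra tests, since total bilirubin is already drawn. There may be a few more pauses and SMC reviews, including for a rise that began early but was first sampled at Week 12, and only for events judged at least possibly related. A letter of amendment needs ethics approval at each site and any other regulatory approval required there. If accrual is fast, few second doses may remain by then.
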